**Study Interventions and Measures:**

The major intervention in this study is the use of ultrasound (US) guidance to assess for correct spinal location prior to epidural placement. This differs from the current standard of care which is to use palpation only to assess for correct spinal location. The outcome measures that will be assessed and evaluated include:

- Total time required for epidural placement\*
- Epidural procedure time\*\*
- Number of epidural attempts needed
- Success rate in the first attempt
- Complication rate including incidence of PDPH and paresthesias
- Incidence of failed epidurals needing to be replaced
- Verbalized patient anxiety and satisfaction levels based on a 1-10 scale
- Modified Woman's Views of Birth Labour Satisfaction Questionnaire (WOMBLSQ) scores

\*Procedure time plus the time needed to locate the puncture site using either palpation or ultrasound guidance, begins when hands or ultrasound probe are applied to the patient

\*\*Time from insertion of the epidural needle to removal of the epidural needle

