This study is to be a prospective, randomized, controlled trial of morbidly obese parturients presenting to either West Penn Hospital or Magee Women's Hospital for delivery and desiring epidural anesthesia. Patients will be screened for participation in the study during the standard pre-anesthesia assessment that is already conducted by anesthesia staff on all patients presenting to Labor and Delivery. Screening will include an evaluation of the patient's medical history and BMI. The study will then be explained to patients who satisfy the inclusion and exclusion criteria and informed consent obtained should they choose to participate. A waiting period of 5-30 minutes will elapse between introduction of the study to the participant's consent to participate. At the time the patient is ready to receive their epidural, an opaque, sealed, numeric envelope labeled only with a study number will be opened containing the data collection sheet and randomly assigned group for that participant. These envelopes will be prepared prior to beginning the study by a healthcare provider not involved in the study. An online randomizer (Randomization.org) will be used to generate a random order for assignment to either the ultrasound guidance group (experimental group) or the palpation only group (control group) which will be revealed to the experimenters only upon opening the envelope at the time of epidural request. These envelopes will be distributed in equal numbers to each facility participating in the study at the onset of the study.

Once the patient has progressed in their labor to the point where they request placement of labor epidural analgesia, the primary investigator for that site ([name] at Magee, and [name] and West Penn) will be the one to open the envelope revealing which group the patient has been assigned to. This will occur during the same hospitalization as the screening visit and in many cases within just a matter of minutes to hours after the initial screening and consent process. This same person will then position the patient in

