their labor and delivery room appropriately for their epidural and then use either the ultrasound machine (experimental group) or palpation (control group) to mark with a marking pen the desired location for epidural placement. [name] and [name] will be the only providers to mark the patients. Every attempt will be made for them to be available for study patients, but if they cannot be (they are caring for another patient or are no longer in the hospital at the time the epidural is requested) then the patient may have to be dropped from the study. Once the patient has been marked, a second anesthesia provider who will be performing the epidural will come into the room. This second provider will be blinded to whether the marks on the patient were made based upon ultrasound guidance or palpation (the patient will not be blinded). This second provider who will perform the epidural can be any type of experienced provider (attending, fellow, resident, or CRNA) who has already completed at least 40 epidurals in the past. They will then perform the epidural in the standard fashion, using the previously marked site as their initial entry point. If entering at the already marked site does not result in success, the provider performing the procedure may reassess and redirect at their discretion. During epidural placement, the primary investigator ([name] or [name]) will be responsible for timing the procedure and recording the number of attempts required to succeed. Epidurals are typically placed successfully within 5-10 minutes depending on patient anatomy and provider experience.

Following the epidural placement and achievement of pain relief, the patient will be asked to rate their satisfaction and anxiety levels during the procedure. No extra interventions or monitoring specific to this study (i.e. outside of what is already normally performed) will be required.

Patients will be followed up on in their hospital room within 24 hours of their delivery to assess for any complications related to their epidural placement and to administer the modified WOMBLSQ questionnaire. If a complication is detected, treatment will be given as clinically warranted. Following that visit no further participation from the patient will be necessary. This study is projected to take about 6 months to complete.

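### The envelope is opened before the woman is positioned, so a step common to both arms is done by someone who knows the arm, and the operator's blind does not cover it

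*Protocol*

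**What the plan says.** The sequence is set out in the Protocol's detailed description of research activities, which follows the heading on screening procedures. When the woman asks for her epidural, the primary investigator at the site "will be the one to open the envelope revealing which group the patient has been assigned to". The text continues "This same person will then position the patient in" and, across a page break, "their labor and delivery room appropriately for their epidural and then use either the ultrasound machine (experimental group) or palpation (control group) to mark" the entry site. The order is therefore reveal, position, mark, all by one person.

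The operator comes later: "Once the patient has been marked, a second anesthesia provider who will be performing the epidural will come into the room". The operator's blind is stated narrowly: "This second provider will be blinded to whether the marks on the patient were made based upon ultrasound guidance or palpation". Meanwhile the investigator "will be responsible for timing the procedure and recording the number of attempts required to succeed".

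Under *Study Interventions and Measures*, procedure time is defined as "Time from insertion of the epidural needle to removal of the epidural needle". Total time adds the time spent locating the puncture site. The SAP makes that total the primary outcome.

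**The concern.** The Protocol describes the intervention as the use of ultrasound, rather than palpation alone, to find the correct spinal location. Positioning belongs to neither technique, and nothing about it requires knowing the arm. As written, the person who does it does know the arm, and the Protocol's *Significance* section states a hope of showing an advantage for ultrasound.

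Extra care with position in one arm, even if unintended, could make the needle pass more or less easily. That would change needle time, the number of attempts and first-attempt success for a reason other than the method of location, and the difference would be credited to ultrasound or to palpation. The documents mention no record of how women were positioned, so an analysis could neither detect such a difference nor adjust for it.

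**Working it through.** **Step 1: which steps need knowledge of the arm, and which does the blind cover?**

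| Step, in Protocol order | Done by | Knows the arm? | Needs to know it? |
|---|---|---|---|
| Open envelope | Site investigator | Yes, from here on | – |
| Position the woman | Site investigator | Yes | No |
| Scan or palpate, and mark | Site investigator | Yes | Yes |
| Place the epidural | Second provider | Blinded to how marks were made | No |
| Time and count attempts | Site investigator | Yes | No |

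Unblinded marking cannot be avoided. Unblinded positioning can, because it sits after the reveal only through the order of the steps. The only standard given for it is a general reference to suitability for the epidural. No posture, checklist or timing relative to the reveal appears elsewhere in either document.

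**Step 2: which outcomes can it reach?** Needle time is a component of total time, the primary outcome. Attempts and first-attempt success are listed under *Secondary Objectives*. All depend on the needle phase, which begins after positioning.

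**Step 3: scale, for illustration only.** There is no figure in the plan to reproduce: the SAP gives neither a standard deviation nor a sample size and defers both to pilot data. It does give a six-minute difference, 80% power and a two-sided alpha of 0.05. Under a normal approximation these fix the standard error of the difference whatever the standard deviation:

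SE = 6 / (1.960 + 0.842) = 6 / 2.802 = 2.14 minutes.

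As a check, assumed standard deviations of 4, 6, 8, 10 and 12 minutes need 14, 32, 56, 88 and 126 women in total. With n per arm, SE = SD × √(2/n). For SD 4 this is 4 × √(2/7) = 2.14, and for SD 12 it is 12 × √(2/63) = 2.14.

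With no true effect and a mean shift of b minutes towards one arm, the chance of a significant result favouring that arm is P(Z > 1.960 − b/2.14):

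| Assumed shift b | b / 2.14 | Threshold | Chance of false claim for the favoured arm |
|---|---|---|---|
| 0 | 0 | 1.960 | 2.5% |
| 0.5 min | 0.23 | 1.73 | 4.2% |
| 1 min | 0.47 | 1.49 | 6.8% |
| 2 min | 0.93 | 1.03 | 15.2% |

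Counting errors in both directions, the overall rate rises from 5% to about 7.5% for 1 minute and 15.5% for 2 minutes. Every value of b is an assumption.

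**The case against.** Five points can be made on the other side.

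- **Nothing shows that position differs by arm, or by how much.** This stands. The Protocol says placement typically takes 5 to 10 minutes, so a 2-minute mean shift would be 2/10 to 2/5, or 20% to 40%, of that. Two investigators would have to sustain it on average. The 0.5-minute row deserves as much weight as the others.
- **The operator may correct a poor position.** This stands in part. The operator has done at least 40 epidurals, works in the usual way, and may think again and change the needle path if the marked site fails. The Protocol neither allows nor forbids repositioning. A reader might infer that the operator is bound to the position found on entering, but the text does not say so. It says only that the operator arrives after positioning and marking.
- **Positioning might start the clock.** A reader could take handling the woman to position her as the moment when timing "begins when hands or ultrasound probe are applied to the patient". The full definition does not support this. It concerns the time needed to locate the puncture site by palpation or ultrasound, so the hands meant are palpating hands. The SAP likewise speaks of ultrasound or palpation time. No timing fault follows.
- **Reordering does not remove the unblinded role.** This stands. The investigator can still adjust the woman while scanning or palpating, and still times and counts. Later repositioning therefore has to be recorded as well.
- **Positioning first could create a new imbalance.** This also stands. The Protocol's section on resources says the machine is kept on the labor and delivery floor. If it were fetched only after the reveal, women in the ultrasound arm would hold position longer.

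**Conclusion.** The point holds as an avoidable risk of performance bias. The Protocol's order places a step common to both arms after the reveal, in the hands of someone who knows the arm, and the operator's blind does not extend to it. Needle time, attempts and first-attempt success are exposed.

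The documents do not support the stronger conclusion that the comparison is biased, or biased towards ultrasound, because they contain no information on size or direction. The error rates above rest on assumed shifts, on no correction by the operator, on a normal approximation, and on a trial sized as the SAP states. They show sensitivity and are not estimates. The case for changing the order is that it reduces the risk at little cost. It is not evidence that the design fails.

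**What to change.** Amend the sequence in the Protocol's description of research activities:

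1. Have the ultrasound machine ready at the bedside for every participant before the envelope is opened.
2. Position the woman as for any epidural.
3. Open the envelope.
4. Scan or palpate, and mark.
5. Record on the data collection sheet any repositioning after the reveal, by whom, and at what stage. The sheet is already inside the envelope, so it is to hand from that point.

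The randomisation paragraph ties opening the envelope to the request for the epidural. Reword it so that the envelope is opened once the woman has been positioned. No particular posture is proposed; that remains a clinical matter.

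**Cost:** a few sentences of wording and one added item on the data sheet. The machine is brought in for control women too, and each woman holds position slightly longer while the envelope is opened. No extra patients, staff or analyses are needed, and no figure in the SAP changes. What remains is that the same investigator still marks, times and counts with knowledge of the arm.

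### Attempts and first-attempt success are recorded by the investigator who knows the arm, and neither document states what counts as an attempt

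*Protocol*

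**What the plan says.** The relevant text is the Protocol's description of research activities, which follows the heading on screening procedures.

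- **Who knows the arm.** The site's primary investigator "will be the one to open the envelope revealing which group the patient has been assigned to". The same person marks the skin using ultrasound or palpation.
- **Who records.** During placement that investigator "will be responsible for timing the procedure and recording the number of attempts required to succeed".
- **Who operates.** After marking, "a second anesthesia provider who will be performing the epidural will come into the room". This person is blinded to the marking method (the patient is not) and may be an attending, fellow, resident or CRNA "who has already completed at least 40 epidurals in the past".
- **What happens after a failed first entry.** The marked site is the first entry point. If it does not succeed, "the provider performing the procedure may reassess and redirect at their discretion".
- **Where the record sits.** The envelope "will be opened containing the data collection sheet and randomly assigned group for that participant".

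Number of attempts and first-attempt success are listed under Study Interventions and Measures and again under Secondary Objectives. In the former section, footnotes define the two time outcomes; nothing defines an attempt. The SAP assigns Fisher's exact test to categorical variables and does not mention the operator.

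**The concern.** First-attempt success depends on where one attempt ends and the next begins. Suppose the needle enters at the mark, is partly withdrawn and re-angled, and then succeeds. That is one attempt under a skin-puncture rule and two under a needle-pass rule. With no stated rule, the investigator who made the mark decides case by case while knowing the method used. If doubtful cases are classed more kindly in one arm, the two outcomes show a difference that the technique did not produce. Operator blinding protects how the needle is handled; it does not protect how the handling is counted. A count made without a rule cannot be reliably reclassified afterwards.

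A second, smaller matter concerns the operator. The Protocol says "Epidurals are typically placed successfully within 5-10 minutes depending on patient anatomy and provider experience", yet neither document says who chooses the operator, or requires the choice before allocation is known. If the choice could follow the envelope, the mix of grades could differ by arm for a reason other than chance.

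**Working it through.** **No figure to reproduce.** The SAP gives 80% power, two-sided alpha 0.05 and a six-minute difference for the primary outcome, but leaves the SD and sample size to pilot data. The main point rests on the text. The arithmetic below only shows what an assumed bias would do.

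**Step 1. Trial sizes.** Per arm, n = 2 × (2.802 × SD / 6)², where 2.802 = 1.960 + 0.842 (normal approximation). All SDs are assumed: 4, 6, 8, 10 and 12 minutes give 7, 16, 28, 44 and 63 per arm.

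**Step 2. An assumed recording bias.** Suppose 20% of placements are ambiguous, and these are classed as first-attempt successes 25 to 50 percentage points more often in the ultrasound arm. The spurious difference is 0.20 × 0.25 = 5 points to 0.20 × 0.50 = 10 points.

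**Step 3. Fisher's exact test at p ≤ 0.05.** The true rate is the same in both arms, and 0, 5 or 10 points are added to the recorded ultrasound rate. Every 2×2 table is enumerated and the probabilities of the rejecting tables are summed.

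| SD (min) | n per arm | True rate 50%: 0 / 5 / 10 points | True rate 70%: 0 / 5 / 10 points |
|---|---|---|---|
| 4 | 7 | 1.3 / 1.4 / 1.9% | 0.7 / 0.7 / 0.8% |
| 6 | 16 | 2.0 / 2.5 / 4.1% | 1.8 / 2.4 / 4.4% |
| 8 | 28 | 2.3 / 3.3 / 6.7% | 2.7 / 3.8 / 8.1% |
| 10 | 44 | 2.5 / 4.2 / 10.1% | 2.8 / 4.9 / 12.7% |
| 12 | 63 | 4.0 / 7.2 / 17.5% | 3.3 / 6.8 / 19.6% |

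The test is conservative, so the unbiased rate is below 5% throughout. At 7 and 16 per arm no case exceeds 5%. At 28 and 44 only the 10-point case does. At 63 both do.

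**Step 4. Operator mix and the primary time.** If operators were selected by arm, bias = (time gap between grades) × (difference in mix). The standard error implied by the SAP's power statement is 6 / 2.802 = 2.14 min. An assumed gap of 1 min and a mix difference of 10 points give 0.1 min and type I error of 5.0%. An assumed gap of 5 min and 30 points give 1.5 min and 10.8%. Chance imbalance in grade is not bias: 200,000 simulated trials with a 5 min gap, a 50:50 mix in both arms, 44 per arm and SD 10 gave 5.0%.

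**Step 5. What adjusting for grade would gain.** With a 5 min gap and a 50:50 mix, grade contributes variance 25 × 0.25 = 6.25. The standard error is multiplied by √(1 − 6.25/SD²): 0.968 at SD 10, 0.909 at SD 6 and 0.781 at SD 4. The reduction is about 3%, 9% and 22%, so it depends on an SD that is not given.

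**The case against.** **First-attempt success is already partly anchored.** The Protocol fixes the mark as the first entry point and separates that from later reassessment. This stands and narrows the gap: what is open is whether a redirection or a later puncture counts as a new attempt. A reader might also infer that no rule exists anywhere. The documents do not support that, because the data collection sheet is not in the file.

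**Nothing shows that the operator is picked after allocation.** This stands. A reader might infer from the order of events that the investigator sees the arm and then selects the operator. The text says only when the operator enters the room; that person may already have been assigned to the patient. The experience minimum and the operator's blinding also limit the effect.

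**The quoted 5-10 minute range does not bound the gap between grades.** This stands. It is a typical range, it mixes anatomy with experience, and it is not stated to be specific to this BMI group. The 5-minute gap, and the 1.5 min and 10.8% derived from it, are assumptions and not ceilings.

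**An operator's own count is self-report and may be too low.** This stands, but any under-count is made without knowledge of the arm if blinding holds. The unblinded patient is in the room and could disclose the arm, so blinding at the time of counting is likely but not assured.

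**The primary time is kept by the same investigator.** It is less exposed, because the clock starts and stops at physical events. The Protocol and SAP word the end of the clock differently; that is a separate matter and is not argued here.

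**Conclusion.** The point holds for the two attempt outcomes. They are recorded by a person who knows the arm, and neither document states a rule for what is counted, although someone blinded to the arm is present. It is a cheap improvement to secondary outcomes, not a threat to the trial's main conclusion. The size of any bias is unknown. The illustrations run from no practical effect (0.7-4.4% at 7-16 per arm) to a substantial one (6.8-19.6% at 63 per arm). They rest on an assumed SD, an assumed true rate and an assumed 5 to 10 point distortion.

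The operator part is weaker. The documents are silent on who chooses and when; that leaves a possible selection route and shows no bias in the primary time.

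**What to change.** 1. Before the first patient, state in the Protocol and on the data sheet which observable event is an attempt: for example each new skin puncture, with redirections through the same puncture recorded separately.
2. Have the blinded operator confirm the count straight after placement, before learning the allocation. Keep the investigator's own count beside it so that disagreements can be seen. Do not have attempts called aloud: the patient could hear, and later "the patient will be asked to rate their satisfaction and anxiety levels during the procedure".
3. As a secondary safeguard, write the operator and grade on a record outside the envelope before opening it (the data sheet is inside), log any later substitution with its reason, and report grade by arm. This narrows the selection route but does not close it. A grade-adjusted sensitivity analysis of total time is optional.

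The cost is wording in the Protocol and data sheet and one extra entry per patient. The same two people are involved and no procedure is added. The operator has to be identified slightly earlier. The time spent locating the site cannot be blinded and is unaffected.

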**Primary Objective (or Aim)**

The primary objective of this study is to determine if using ultrasound guidance for epidural catheter placement is associated with a reduction in the total time required in epidural catheter placement.

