Use of Ultrasound Guidance to Assist with Labor Epidural Placement in Patients with a BMI ≥ 40

NCT02984267

Date: 10/1/2016

Statistical analysis plan

The primary outcome is total time (minutes) to successful epidural catheter placement, defined as the sum of the ultrasound or palpation time, plus the epidural catheter placement time. The present study focused on the morbidly obese population ($BMI \geq 40$), of which we are unaware of any available data to guide a calculation for the primary outcome. Based on pilot data means and variances, total sample size will be calculated with 80% power to detect a six-minute difference in time-to-placement between groups with an alpha of 0.05 (two-tailed).

Distribution normality of continuous data will be examined using box plots and histograms. Non-normally distributed data will be compared using the Kruskal-Wallis H test, and continuous data compared with the Mann-Whitney U test. Normally distributed continuous variables will be compared using the independent sample Student t-test. The Fisher Exact test will be used for categorical variables. A P-value of ≤ 0.05 will be considered statistically significant.

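### The investigator who opens the envelope and marks the woman also times the procedure, so the needle phase of the primary endpoint is timed unblinded; no one else is named to time the locating phase, which cannot be blinded.

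*Protocol*

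**What the plan says.** The primary objective (Protocol, Primary Objective) asks whether ultrasound guidance "is associated with a reduction in the total time required in epidural catheter placement". The SAP makes total time the primary outcome, "defined as the sum of the ultrasound or palpation time, plus the epidural catheter placement time". The footnotes under Study Interventions and Measures say that the total-time clock "begins when hands or ultrasound probe are applied to the patient", and define epidural procedure time as "Time from insertion of the epidural needle to removal of the epidural needle".

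The roles are set out in the Protocol's description of research activities, which follows the list of screening procedures:

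- **Allocation.** The site's primary investigator "will be the one to open the envelope revealing which group the patient has been assigned to".
- **Locating and marking.** That same person positions the woman, then scans or palpates and marks the site. The two site investigators are the only people who mark.
- **Needle placement.** "Once the patient has been marked, a second anesthesia provider who will be performing the epidural will come into the room". This provider is blinded to how the mark was made; the patient is not.
- **Timing.** During placement the site investigator "will be responsible for timing the procedure and recording the number of attempts required to succeed".

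Neither document describes an independent timekeeper, recorded clock times, or confirmation of the times by the operator.

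**The concern.** The Protocol blinds the operator, which guards against expectation affecting how the needle is placed. It then gives the measurement of that phase to the one member of the study team who certainly knows the arm and who made the mark being tested. Calling needle-in or needle-out slightly early or late, differently by arm, would go straight into the primary outcome. If only a duration is written down, nobody could detect this later.

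The locating phase is the part of total time that differs between arms by design. Its clock starts with the investigator's own act, and the documents do not say who reads that clock.

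This point concerns who measures the endpoint. How an attempt is counted and what the clock should include are separate questions.

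**Working it through.** **Step 1: trace the roles.** No arithmetic applies here; the passages are set side by side.

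| Part of total time | Knows the arm | Does the act | Named to time it |
|---|---|---|---|
| Locating and marking | Site investigator, and anyone else present | Site investigator | No one; the timing sentence covers only the period of epidural placement |
| Needle in to needle out | Site investigator (the operator is blinded) | Second provider | Site investigator |

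Unblinded timing of the needle phase is explicit. For the locating phase there is a gap: the investigator is the only person given any timing duty, and the operator arrives after marking. A helper with a watch is not excluded, but would see the probe or the hands.

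**Step 2: put a scale on it.** There is no figure in the plan to reproduce. The SAP gives a six-minute difference, 80% power and two-sided alpha 0.05, but no SD and no N, because N is to come from pilot data. The SDs and the timing shifts below are therefore assumptions. The calculation is a two-sample t-test with the noncentral t distribution.

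*Sample size.* The smallest n per arm giving at least 80% power for 6 minutes is 17, 29, 45 and 64 for SDs of 6, 8, 10 and 12 minutes.

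*Effect of a shift.* SE = SD × √(2/n). With SD 8 and n = 29, SE = 8 × √(2/29) = 2.10 minutes. Let b be the systematic timing difference between arms.

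- No true effect: noncentrality = b/SE. For b = 1 this is 1/2.10 = 0.48.
- True effect of 6 minutes with the shift against ultrasound: noncentrality = (6 − b)/SE. For b = 1 this is 5/2.10 = 2.38.

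| Assumed shift b (min) | Type I error | Power, shift against ultrasound |
|---|---|---|
| 0 | 5.0% | 80% |
| 0.25 | 5.2% | 77% |
| 0.5 | 5.6% | 73% |
| 1 | 7.5% | 65% |
| 2 | 15.5% | 46% |

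**Step 3: check that the assumed SD matters little.** Fixing 80% power at 6 minutes fixes the ratio of effect to standard error at about 1.960 + 0.842 = 2.80, so a shift of b moves the test statistic by about 2.80 × b/6 whatever the SD. This normal approximation gives type I errors of 5.6%, 7.5% and 15.4% for 0.5, 1 and 2 minutes, and power of 73%, 65% and 46%. In the exact calculation the type I error varies by no more than about 0.002 across SDs of 6 to 12 (at 2 minutes, 0.156 for SD 6 against 0.155 for SD 8).

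**The case against.** The strongest reply has four parts.

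1. **The locating phase cannot be blinded.** Anyone in the room sees a probe or hands. This stands. It limits what any fix can do and is no fault of the plan.
2. **The needle events are observable.** Needle insertion and removal are defined and are performed by a blinded operator, so the timer has limited latitude. This largely stands, and makes shifts of seconds more plausible than shifts of minutes. A 15-second shift raises the type I error only to 5.2%. Two minutes would be a third of the target difference, and 20% to 40% of the 5 to 10 minutes that the Protocol gives as typical for placement.
3. **The power loss needs a shift against ultrasound.** The Protocol's Significance section hopes to show a practical advantage for ultrasound, so that direction is not the obvious one. This stands; the documents support no direction.
4. **Time stamps do not blind anyone.** This is true of the locating phase. For the needle phase, the operator's call and initials bring in a blinded person who at present has no role in the timing.

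Two stronger readings are tempting. A reader might infer that the investigator must time his or her own scanning or palpation. That is likely by elimination, but no sentence says it. A reader might also infer that the timers designed the trial and have a stake in its result. No passage says who designed it, and the Background section says the West Penn investigator was a later replacement.

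**Conclusion.** The concern holds in a limited form. It is explicit that the needle phase of the primary endpoint is timed by a person who knows the arm, and that the blinded operator has no part in the timing. It is also clear that no one is named to time the locating phase.

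The documents give no evidence that bias occurred. The illustrated range runs from almost nothing (5.2% type I error, 77% power at 0.25 minutes) to material (15.5% and 46% at 2 minutes). It rests on assumed shifts and SDs, on a trial sized for exactly the SAP's target, and on the t-test being the analysis used; the SAP provides for a rank test if the data are not normal. The case for acting is that the safeguard costs little and a timing error cannot be reconstructed afterwards, not that a large bias is likely. This is a cheap improvement, not an error in the plan.

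**What to change.** Add four clock-time fields (hh:mm:ss), all read from one continuously running clock, to the data collection sheet already placed in each envelope: first contact of hands or probe, mark finished, needle insertion, and final needle removal.

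- State in the Protocol who records the two locating stamps.
- Have the blinded operator call needle insertion and final removal aloud, and initial those two stamps before leaving the room.
- Compute total time at analysis as (mark finished − first contact) + (final needle removal − needle insertion), which follows the SAP's sum, so that no duration is entered by hand.
- Report epidural procedure time, already a planned outcome, beside the primary result as the component confirmed by a blinded person.

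**Cost.** Four fields and one instruction, with no extra staff. The operator must call and initial two times. The Background section says West Penn had not begun enrolling, so that site at least could use the sheet from its first patient.

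**Limit.** The locating phase remains unblinded. The stamps make it traceable and no more.
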